This is a Phase 2, Prospective, Randomized, Multicenter, Open-Label, Controlled Trial. Patients are randomized to treatment with Exenatide SR + SOC vs. SOC alone at 4 months or 12 months post transplant after kidney transplantation and followed until 24 months after kidney transplantation. Patients who discontinued medication for AEs will be contacted within 30 days to follow up on the resolution of symptoms.

Study participants with prediabetes at 4 months or 12 months after kidney transplantation will be randomized 2:1 to receive either Exenatide SR or diet and exercise only with no medication. We plan to enroll approximately 50% of subjects at 4 months post transplant and 50% of subjects at 12 months post transplant

Primary Endpoint is the incidence of diabetes at 24 months after kidney transplantation.

Patients will be followed for 2 years after transplantation (20 or 12 months after enrollment) for progression to all endpoints. Therefore, there will be three SOC biopsies—4, 12 and 24 months after transplantation. Hemoglobin A1C will be performed at the same time points. In addition 2hOGTT will be performed if clinically indicated per our SOC.

Study Sites: This is a multicenter study involving the three Mayo Clinic kidney transplant programs. This group has a common IRB and can contract centrally. Collectively, they perform approximately 600 kidney transplants per year. They have a history of multicenter research trials—they enrolled 480 patients along with a fourth center in a recent NIH-sponsored trial that required a 1 year kidney biopsy (NCT01782586 Validation of Gene Expression Markers of Renal Allograft Functional Decline (<https://clinicaltrials.gov/ct2/show/NCT01782586?term=[name]&rank=10>)). Thus, this consortium is large enough to ensure enrollment in the time frame suggested, yet small enough to ensure collaboration and uniformity needed for these studies.

The patient visits and follow-up including safety laboratories all fall within the SOC follow-up at all sites. These include the biopsies. All clinical standard of care labs and biopsies are followed by clinical operating protocols and are followed by clinical nursing and physician staff.

Study drug:

Exenatide SR

Background.

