(DMGS). 77% of patients with diabetic nephropathy on 10 year biopsy did not have diabetes pre-transplantation, and 46% were in patients without overt diabetes pre- or post-transplantation, but with characteristics of prediabetes including fasting hyperglycemia and obesity. Furthermore, kidney transplants with DMGS had greatly inferior graft survival (Figure 1). These data suggest that a paradigm shift is needed to improve the long-term graft survival for kidney transplants.

PTDM is a pervasive problem. In a review of UTHSA kidney transplant recipients, the incidence of PTDM was 43% among Hispanics and 33% in non-Hispanic whites. Patients with PTDM had a higher BMI (BMI=30.4 kg/m²) compared with patients without PTDM (BMI=27.7 kg/m²). Based on preliminary data from our collaborative analysis of the University of Michigan Transplant Center cohort, 15% of 345 kidney transplant recipients who did not have diabetes pre-transplant had developed PTDM based on an OGTT done at 6 months post-transplant, and another 24% were prediabetic based on 2-hour glucose values which met the criteria for IGT. Similarly, the Mayo experience (a predominantly Caucasian population) noted a 33% incidence of IFG at 1 year among kidney transplant recipients without diabetes pre-transplant.

Study endpoints

Primary Efficacy Endpoint:

Incidence of diabetes at 24 months after kidney transplantation.

Diabetes is defined based on ADA criteria for diagnosis of diabetes;

HbA1C>6.5%

or FPG>126 mg/dl (fasting is defined as no caloric intake for at least 8 hours)

or 2h plasma glucose >200 mg/dl during an OGTT

or random plasma glucose >200 mg/dl in patient with classic symptoms of hyperglycemia

Based on published data, we expect that 30% of untreated patients with prediabetes at 4 months will develop diabetes by 12 months after transplantation. See statistical assessment section.

Patients also will be followed up to 20 months after enrollment for progression to other endpoints

Secondary endpoints

- To evaluate the prevention of progression to diabetes by 24 months after transplantation
- To evaluate the safety and tolerability of Exenatide SR
- To compare hemoglobin A1c levels in patients treated with Exenatide SR + SOC vs. SOC alone at 24 months after kidney transplantation.
- To compare the incidence of mesangial expansion >20% in patients treated with Exenatide SR + SOC vs. SOC alone at 24 months after kidney transplantation.

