Safety will be assessed using incidence of all adverse events (AEs), serious adverse events (SAEs), treatment-emergent adverse events (TEAEs) and AEs leading to study withdrawal; review of laboratory data, including hematology, renal function, biochemistry and microbiology and malignancies; new concomitant medication usage; hospitalization rates; and vital signs. Adverse events will be classified for serious adverse events using standard regulatory criteria.

Statistical analysis plan.

Study design and analysis will be performed according to intention to treat principles. Time to development of PTDM will be compared utilizing Kaplan-Meier curves generated according to the product limit method utilizing log-rank tests to evaluate intergroup differences. Risk adjustment for baseline differences between groups will be assessed according to multivariate proportional hazards models. Data on patients who withdraw or are lost to follow-up will be censored at the time of last visit. Comparisons of repeated measures between groups including the secondary endpoints outlined above will be performed utilizing general linear mixed models with transformation of data to logarithm forms when appropriate. These comparisons will be made with inclusion of subjects who withdraw within the follow-up period. Sensitivity analysis excluding these patients will also be performed.

Needed sample size was calculated according to development of PTDM based on utilization of a 2-sided chi-squared test at a 5% significance level and 80% power. The incidence of PTDM reported after kidney transplant varies from 2-50% with best estimates indicating that approximately 30% of patients will develop PTDM.^{3,4,41,42} The SCALE trial comparing GLP-1 receptor agonists to placebo showed an 80% reduction in development of type 2 diabetes.²¹ Other clinical trials evaluating prevention of diabetes showed a 30% risk reduction with metformin and 55-72% reduction with TZDs.^{29,43} Thus, sample size was calculated based on a proportion of 30% incidence of PTDM in the control group and 80% risk reduction in the experimental group (consistent with SCALE trial). A total of 81 (54:27 according to 2:1 randomization) patients will be required to achieve the power and significance levels above. In our preliminary data, 24-33% of kidney transplant recipients meet prediabetes criteria. We would expect that full enrollment would take 24 months.

Data management plan

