The coordinating center will be the primary contact for this study and the data coordinating center: [name] and his program coordinator, M [REDACTED] L [REDACTED] ([REDACTED] and [contact])

1. The FDA investigator-initiated IND will be held by [name]
2. Contracts will preferentially be through the Coordinating Center with subcontracts to the other sites. Indirect costs will be charged only once (i.e. at the site where the funds are actually spent).
3. Protocols will be approved by local IRB (the three Mayo sites have a central IRB).
4. Data is entered into a common database with case-report forms similar to any FDA studies(MEDIDATA Rave case forms specific for transplant are already in place)
5. The Coordinating Center will be responsible for data cleanup, data reporting and reporting to the sponsors and the FDA.
6. Histology:
Mesangial expansion by light microscopy

Schedule of visits

Enrollment Day 122 (4 months)

	Enrollment Day 122 after KTx range 90-180 days	Day 7±3 Days Post enrollment	Monthly labs to 1 year per SOC	Day 90±7	Day 365 ±90 after KTx	Labs q3 months from 12-24 months	Day 730 ± 90 after KTx
Consent	x						
Labs	x	x	x		x	x	x
Clinic visit	x				x		x
Communication through phone call or EMR		x		x		x	
HgbA1c					x	x	x
Biopsy	x				x		x
Pregnancy test	x						

Enrollment Day 365 (1 year)

	Enrollment Day 365 after KTx range 300-420 days	Day 7±3 Days Post enrollment	Labs q 3 months per SOC	Day 90±7	Day 730 ± 90 after KTx
Consent	x				
Labs	x	x	x		x
Clinic visit	x				x
Communication through phone call or EMR		x		x	
HgbA1c					x
Biopsy	x				x
Pregnancy test	x				

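### The text schedules HbA1c at enrolment but neither visit table marks it, and the 24-month HbA1c model does not say whether or how baseline enters

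*Combined protocol and SAP*

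**What the plan says.** Under Secondary endpoints, the HbA1c item is "To compare hemoglobin A1c levels in patients treated with Exenatide SR + SOC vs. SOC alone at 24 months after kidney transplantation". It concerns a level at 24 months; neither a baseline value nor a change from baseline is mentioned.

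The Statistical analysis plan section covers it with one general sentence: "Comparisons of repeated measures between groups including the secondary endpoints outlined above will be performed utilizing general linear mixed models". That section lists no covariates, no month-24 contrast and no role for entry cohort. The only adjustment it plans concerns time to diabetes: "Risk adjustment for baseline differences between groups will be assessed according to multivariate proportional hazards models". The covariates for that model are not named either.

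On timing, Study design/schedule sets biopsies at 4, 12 and 24 months and adds: "Hemoglobin A1C will be performed at the same time points". Those times include both enrolment points. In Schedule of visits, HbA1c has its own row, separate from the row for labs. In the 4-month table it is marked at Day 365, at the three-monthly labs from 12 to 24 months, and at Day 730. In the 12-month table it is marked at Day 730 only. The enrolment column is blank for HbA1c in both tables, including the one headed "Enrollment Day 365 after KTx range 300-420 days".

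The Inclusion criteria accept fasting glucose, 2-hour glucose or HbA1c (5.7-6.4%) as evidence of prediabetes, so eligibility alone does not guarantee an HbA1c result.

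**The concern.** Two gaps compound each other. First, text and tables disagree on whether HbA1c is taken at enrolment. A site working from the tables could randomise a patient who qualified on glucose and hold no pre-treatment HbA1c. In the 4-month cohort, every HbA1c marked in the table is after randomisation, so none of those values can stand in for baseline. In the 12-month cohort, the table gives a single value, which leaves a repeated-measures model with nothing repeated.

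Second, even where the value exists, the plan does not say what the model does with it. With 27 patients on standard care, spread between patients dominates the error, and a chance difference between arms at baseline can carry through to month 24. Precision and protection against that imbalance are both at stake, and the decision is left until after the data are seen.

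Kidney function has the modelling gap only. An eGFR limit applies at entry and labs are marked at enrolment in both tables, so the baseline should exist, but its use in the model is not stated.

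**Working it through.** **Inputs from the documents** (Statistical analysis plan section): "2-sided chi-squared test at a 5% significance level and 80% power"; "30% incidence of PTDM in the control group and 80% risk reduction in the experimental group", that is 0.30 against 0.30 × 0.20 = 0.06; and "A total of 81 (54:27 according to 2:1 randomization) patients will be required". For HbA1c the documents give no SD, correlation, target difference or power.

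**The plan's own figure.** Pooled two-proportion formula, 2:1 allocation, no continuity correction, with pooled proportion (0.30 + 2 × 0.06)/3 = 0.14:

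n(control) = [1.96·√(0.14 × 0.86 × 1.5) + 0.842·√(0.30 × 0.70 + 0.06 × 0.94/2)]² / 0.24² = 26.9, rounded up to 27.

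This gives 27 + 54 = 81, so the stated number reproduces (power 80.2%). It concerns diabetes, not HbA1c, but fixes the arm sizes used below.

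**Unadjusted month-24 comparison.** In SD units the standard error is √(1/27 + 1/54) = 0.236. The difference detectable with 80% power is (1.96 + 0.842) × 0.236 = 0.660 SD.

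**Chance imbalance.** The standard error of a baseline difference between arms is the same 0.236 SD. The probability that it exceeds 0.3 SD in either direction is 2 × [1 − Φ(0.3/0.236)], about 20%.

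**Adjusted for baseline.** Residual variance is (1 − r²) × SD², so the detectable difference is 0.660 × √(1 − r²). The value of r is an assumption.

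| Assumed r | Variance removed (r²) | Detectable difference (SD) | Power for 0.5 SD |
|---|---|---|---|
| 0 (unadjusted) | 0% | 0.660 | 56.4% |
| 0.3 | 9% | 0.630 | 60.4% |
| 0.4 | 16% | 0.605 | 63.9% |
| 0.5 | 25% | 0.572 | 68.8% |
| 0.6 | 36% | 0.528 | 75.5% |
| 0.7 | 49% | 0.472 | 84.4% |

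Estimating one extra coefficient multiplies the variance by about 1 + 1/77 = 1.013, a cost of roughly 1.3%. The table does not deduct this cost and assumes no dropout.

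**Effect of the entry window.** Selecting on HbA1c narrows the baseline spread and lowers the correlation. If u is the ratio of restricted to unrestricted baseline variance, the fraction removed becomes r²u/(r²u + 1 − r²).

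Example: assume a normal baseline with mean 5.7 and SD 0.5, truncated to 5.7-6.4%, which is 0 to 1.4 SD above the mean. Then u = 1 − 0.500 − 0.353 = 0.147. For unrestricted r = 0.5 the fraction is 0.25 × 0.147/(0.25 × 0.147 + 0.75) = 4.7%.

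Over assumed means of 5.5-5.9, SDs of 0.4-0.6 and unrestricted r of 0.5-0.71:

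- All patients within 5.7-6.4%: about 3% to 18% removed. The detectable difference is 0.660 × √0.97 = 0.65 SD down to 0.660 × √0.82 = 0.60 SD.
- Only the 6.4% ceiling binding, since glucose-qualified patients may lie below 5.7%: about 16% to 48% removed.

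A lower unrestricted r would give less in either case.

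**The case against.** The strongest reply is that the baseline probably exists for most patients. The design text schedules it, labs are marked at enrolment in both tables, entry requires laboratory evidence of prediabetes and excludes diabetes, and Specific Methods lists HbA1c among the tests for both states. A repeated-measures mixed model could also carry the enrolment value as a response or a covariate. The endpoint is secondary and has no power claim.

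Much of this stands, and it rules out several stronger readings that a reader might infer:

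- *The plan leaves baseline HbA1c out.* It does not say so; it is silent.
- *Half the trial has no baseline.* About half of the patients are to enter at 12 months, but this would follow only if the tables overrode the design text. The documents show a contradiction and a risk for patients who qualify on glucose, not a known loss.
- *Adjustment removes a quarter to a half of the variance.* That is r² for r of 0.5 to about 0.7. The documents support no particular r, and the entry window may lower it.
- *Covariates in the diabetes model will be picked by observed imbalance.* The sentence on risk adjustment names none and gives no selection rule.

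The comparator also matters. The gains above are against an unadjusted month-24 comparison. If the planned mixed model already uses baseline, part or all of the gain is already there.

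The reply does not remove the conflict between text and tables, or the plan's silence on how baseline enters. A pre-treatment value that is missed cannot be obtained later.

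**Conclusion.** The point holds as a scheduling contradiction joined to an unspecified model. Text and tables disagree on enrolment HbA1c, some glucose-qualified patients could end up without a baseline, and the month-24 analysis does not say whether or how baseline enters.

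The benefit of settling this is real but of uncertain size: 9% to 49% of variance for an assumed r of 0.3 to 0.7, and perhaps only about 3% to 18% if every patient lies within 5.7-6.4% (unrestricted r of 0.5 to 0.71). Both ranges are relative to an unadjusted comparison at 54:27 with no dropout. Pre-specified adjustment also deals with chance baseline imbalance, whatever its size.

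The change is worth making, but it does not threaten the primary result, and the sample size of 81 is unaffected. A reader might infer a useful power gain for the diabetes endpoint too. The documents do not say how strongly baseline HbA1c predicts progression, and no material gain is claimed there.

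**What to change.** 1. Mark HbA1c in the enrolment column of both visit tables, so that they agree with Study design/schedule.
2. State in the statistical analysis plan that the HbA1c estimate is the treatment contrast at month 24, adjusted for baseline HbA1c and entry cohort (4 or 12 months). Use either ANCOVA or a mixed model in which baseline is a response with a common mean across arms.
3. Specify the kidney-function comparison in the same way, with enrolment eGFR as baseline.

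The cost is two table marks, a few sentences and about one degree of freedom per covariate. The design text already commits to HbA1c at both enrolment times, and the notes below the tables describe all labs except the pregnancy test as standard of care, so no additional study-funded test is expected.

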All labs are standard of care, except for the pregnancy test. Day 7 labs represent current practice of repeating labwork with any significant changes in medical therapy. Day 7 labs will include CBC, basic metabolic panel (BMP), which includes creatinine, BUN and electrolytes and immunosuppression levels, including Tacrolimus level and MPA (CellCept). CBC, BMP and Tacrolimus levels will be performed monthly thereafter up to 12 months post transplant and q3 months indefinitely. All labs obtained are standard clinical labs per local practice and monitored by the licensed clinical nurses or physicians following the patient's clinical care. Additional labs will be done as dictated per current standard of care. If there is a lab value out of reference, study staff would also bring it to the clinical staff's attention, but research staff would not dictate or change the clinical care of the patient unless it was directly related to study drug and were directed by the PI/Co-PI

Publication plan. Results will be written up for publication and submitted to a transplant journal such as the American Journal of Transplantation or Transplantation. Similar to prior studies, we also will submit this data as an abstract/oral presentation to the American Transplant Congress annual meeting.

POTENTIAL CHALLENGES: Performing this initial trial within the Mayo sites represents crucial evidence needed to determining the efficacy as well as safety and tolerability of GLP-1 receptor agonists in the

transplant population. Other trials are required to investigate the efficacy of these anti-diabetic medications in other solid organ transplant recipients such as liver transplant patients who also experience a high incidence of PTDM.

Determining significance in longitudinal changes in allograft protocol biopsies related to diabetic nephropathy in prediabetic patients is beyond the scope of this trial. However, this data based on samples collected per standing clinical protocols will provide innovative and generalizable knowledge related to the renal changes in prediabetics that has otherwise not been available. The preliminary data obtainable through the exploration of this specific aim will be of great value in broadening the scientific knowledge related to the relationship between prediabetes and diabetic nephropathy and determining key endpoints for designing future diabetes prevention trials in solid organ transplant recipients.

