FUTURE DIRECTIONS: Given the pervasiveness of diabetes and prediabetes in kidney and other solid organ transplant recipients, well-designed clinical trials aimed at determining best therapy for preventing and improving treatment of diabetes after transplantation are desperately needed. The concomitant use of diabetogenic agents, including corticosteroids and calcineurin inhibitors, and the common weight gain experienced after transplant create a challenging environment to deal with these problems, but also emphasizes the importance of addressing these concerns. The completion of a prospective, feasibility trial will help obtain needed data about the safety, tolerability, and efficacy of GLP-1 receptor agonists in kidney transplant recipients and specifically Hispanic patients. Improved treatment of prediabetes and diabetes after kidney transplantation may portend the realization of goals to enhance long-term kidney graft outcomes, as well as improve the health and survival of these patients.

Specific Methods.

Prediabetes and diabetes are determined using standard serum blood glucose level determinations including: fasting serum glucose, 2 hour post serum glucose in an OGTT and HbA1c.

eGFR is based on serum creatinine levels using MDRD⁴⁸

Light Microscopy

Light microscopy will be used to determine the percentage of (1) global glomerulosclerosis (GGS) involving >20% of the glomeruli (GGS; 0 = 0%, 1 = ≤20%, 2 = >20%); and (2) mesangial matrix expansion (or mesangial sclerosis, MS) as defined as mild (1), moderate (2) and severe (3) averaged over all of the glomeruli in each biopsy sample

- 2. *2015 USRDS annual data report: Epidemiology of Kidney Disease in the United States*. Bethesda, MD: National Institutes of Health, National Institute of Diabetes and Digestive and Kidney Diseases;2015.

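### The only between-arm histology endpoint is a yes/no at >20% mesangial expansion, although a score averaged over glomeruli is already read; no listed endpoint compares that score, and >20% is not defined on its scale

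*Combined protocol and SAP*

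**What the plan says.** The same histology item stands under Study objectives (Secondary) and under Study endpoints (Secondary endpoints): "To compare the incidence of mesangial expansion >20% in patients treated with Exenatide SR + SOC vs. SOC alone at 24 months after kidney transplantation". It is the only between-arm histology comparison in either list.

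Specific Methods, Light Microscopy, describes two readings. The first is "global glomerulosclerosis (GGS) involving >20% of the glomeruli", coded 0, 1 or 2 with a boundary at 20%. The second concerns the mesangium, with expansion "as defined as mild (1), moderate (2) and severe (3) averaged over all of the glomeruli in each biopsy sample". The second reading yields a graded score for each biopsy, and no percentage is attached to it.

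The Statistical analysis plan sizes the trial on post-transplant diabetes only. It assigns repeated measures, secondary endpoints included, to general linear mixed models, and it names no test for the histology proportion. Under Potential Challenges the protocol states: "Determining significance in longitudinal changes in allograft protocol biopsies related to diabetic nephropathy in prediabetic patients is beyond the scope of this trial".

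**The concern.** Two things do not fit together.

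- **Information is read but not used.** A grade averaged over many glomeruli takes many values. A yes/no keeps only the side of the line on which a patient falls. A graft just under the line counts the same as one with no expansion, and a graft just over it counts the same as severe disease. With few grafts over the line, the comparison rests on a handful of events in 27 versus 54 patients.
- **The line is not on the scale.** Mesangial expansion is scored on grades 1 to 3. The only 20% boundary in Specific Methods belongs to global glomerulosclerosis. Two readers could therefore classify the same biopsy differently against the endpoint.

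Changes in the allograft related to diabetic nephropathy are the third of the three stated aims. At stake is how precisely the trial can estimate a drug effect on histology from biopsies it will collect in any case.

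**Working it through.** **1. The plan's own sample size.** Inputs from the Statistical analysis plan: "2-sided chi-squared test at a 5% significance level and 80% power"; "a proportion of 30% incidence of PTDM in the control group and 80% risk reduction in the experimental group"; 2:1 allocation. The treated rate is 0.30 × (1 − 0.80) = 0.06, and the pooled rate is (0.30 + 2 × 0.06)/3 = 0.14.

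Control n = [1.960 × √(0.14 × 0.86 × 1.5) + 0.842 × √(0.30 × 0.70 + 0.06 × 0.94/2)]² / 0.24² = 26.9, rounded up to 27. With 54 treated the total is 81, which matches "A total of 81 (54:27 according to 2:1 randomization) patients will be required". The approximate power is 80.2%. This figure concerns diabetes only; the documents state no rate, effect, SD or power for histology.

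**2. Yes/no versus score, normal case.** All inputs here are assumptions except 27:54 and the two-sided 5% level. The score is normal, the drug lowers it by 0.6 SD, and a proportion p of the standard-of-care (SOC) arm lies above the cut.

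- Treated rate: q = Φ(Φ⁻¹(p) − 0.6). For p = 20%: Φ(−0.842 − 0.6) = Φ(−1.442) = 7.5%.
- Expected events at p = 20%: 27 × 0.20 + 54 × 0.0747 = 5.4 + 4.0 = 9.4.
- Power of the yes/no: the summed binomial probability of all tables (x, y) with |x/27 − y/54| / √[r(1 − r)(1/27 + 1/54)] > 1.96, where r = (x + y)/81.
- Power of the score: a t-test with non-centrality 0.6/√(1/27 + 1/54) = 0.6/0.2357 = 2.55 on 79 degrees of freedom, which gives 71%. It stands in for the rank test, which gives up a little to it on normal data.

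| SOC rate above cut | Treated rate | Expected events, both arms | Power, yes/no | Power, score | Difference |
|---|---|---|---|---|---|
| 10% | 3.0% | 4.3 | 28% | 71% | 43 points |
| 20% | 7.5% | 9.4 | 38% | 71% | 33 points |
| 35% | 16.2% | 18.2 | 48% | 71% | 23 points |
| 50% | 27.4% | 28.3 | 52% | 71% | 19 points |

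If 15% of biopsies are missing (27 × 0.85 ≈ 23; 54 × 0.85 ≈ 46), the 20% row becomes 32% versus 64%.

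**3. Information kept by the cut.** For a normal score the large-sample efficiency is φ(z)²/[p(1 − p)] with z = Φ⁻¹(p). It is 34% at p = 10%, 49% at 20%, 60% at 35% and 64% at 50%. More than half is lost only when the rate is below about 20%.

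**4. Where the gain shrinks.** Simulations of 15 glomeruli graded 0 to 3 and averaged, at 54:27, compared a rank test on the average with chi-squared on the cut. The grade 0, the 15 glomeruli and the shifts are assumptions.

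| Biopsies scoring zero | SOC rate above cut | Shift (SD) | Rank test | Yes/no |
|---|---|---|---|---|
| 36% | 9% | 0.7 | 70% | 33% |
| 36% | 31% | 0.7 | 71% | 56% |
| 68% | 32% | 0.5 | 38% | 35% |
| 83% | 17% | 0.7 | 43% | 42% |

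With 73% to 86% zeros and the cut near any expansion, the gain was about 0 to 4 points. A cruder single 0 to 3 grade per biopsy, with shifts of 0.4 to 0.8 SD, gave the same pattern: a loss of about 0 to 5 points with the cut at grade 1 or more, and about 7 to 32 points at grade 2 or more. So the size of the loss depends on the mapping that the protocol leaves open.

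**The case against.** The strongest reply has four parts.

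- **Scope.** The protocol says "Determining significance in longitudinal changes in allograft protocol biopsies related to diabetic nephropathy in prediabetic patients is beyond the scope of this trial" and presents the biopsy data as preliminary. This lowers the priority. It does not remove the between-arm comparison to which both secondary lists commit. The same section wants these data to help choose endpoints for future trials, and an effect estimate on the score serves that purpose.
- **Mixed models.** The Statistical analysis plan could be read as allowing a graded analysis. It does not exclude one. But the sentence concerns repeated measures, the listed endpoint is an incidence at one time point, and nothing commits the trial to the score. In an open-label trial a score analysis chosen later would be post hoc.
- **Clinical meaning.** The preliminary data link the presence of diabetic glomerulosclerosis to graft survival, so a yes/no has a clinical rationale. That is a good reason to keep reporting the proportion, but not to make it the only comparison.
- **Size.** The loss can be close to nil, as step 4 shows. This stands, and no minimum loss can be claimed.

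A reader might go further and infer that the averaged score itself is cut at 20%. The documents do not say so. Nor do they show that the yes/no discards most of the information, or that a real effect would usually be missed: both depend on an unstated 24-month rate. In some of the assumed settings the yes/no has better than even power, and in others the score analysis is itself below 50%.

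**Conclusion.** The concern holds in a limited form. It is firm from the text alone that the single listed between-arm histology endpoint is a yes/no, that a finer score is read but not compared, and that the threshold is undefined on the scale of that score.

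The cost in power is conditional. It is 19 to 43 points under a normal score with a 0.6 SD shift, all 81 biopsies readable and SOC rates of 10% to 50%. It is about 0 to 4 points if most biopsies score zero and the cut is near any expansion. The nearest rate in the documents, 35% with diabetic mesangial glomerulosclerosis, is at 10 years and does not narrow this range. The score analysis was not materially worse in any setting tried, so the change carries little statistical risk. It is a low-to-moderate priority improvement to a secondary endpoint, and its main benefit is a more precise effect estimate.

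**What to change.** In both secondary lists (Study objectives and Study endpoints):

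- Prespecify the between-arm comparison of the 24-month mesangial score averaged over all glomeruli. Use a Wilcoxon rank-sum test with a Hodges-Lehmann difference, or a proportional-odds model with a common odds ratio, in either case with a 95% confidence interval.
- In Light Microscopy, define >20% mesangial expansion on the scale that is read, including how a glomerulus with no expansion is scored, and reconcile it with the 20% boundary that now belongs to global glomerulosclerosis.
- Once it is defined, report the >20% proportion by arm as a descriptive summary.

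The cost is wording only: no new biopsy, reading or patient. The downside is that a shift in score is less direct for clinicians than a proportion, which is why the proportion is still tabulated.
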